#### 13.8.1 Adverse Events

All AEs will be coded using the Medical Dictionary for Regulatory Activities (MedDRA) (version 15.1 or higher).

Adverse events occurring from the signing of informed consent and prior to the initiation of study drug treatment (pretreatment AEs) will be summarized.

Treatment-emergent AEs are AEs that begin after the start of ORGN001. Treatment-emergent AEs will be summarized by incidence, Preferred Term, System Organ Class (SOC), seriousness, severity, relationship to treatment.

All AEs will be summarized by both event counts and patient counts. For patient counts, if a patient has more than one occurrence of an AE for a specific Preferred Term or SOC, the patient will be counted only once for that Preferred Term or SOC. The most severe occurrence of an AE as well as the most extreme relationship of the AE will be indicated in cases of multiple occurrences of the same AE at onset of the AE.

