3.1. Changes from Analyses Specified in the Protocol

Not applicable.

[REDACTED]

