6.5.3. Adverse Events

Adverse events will be classified by system organ class (SOC) and preferred term (PT) using of MedDRA (version 22.0). The severity/relationship will be assessed.

The AEs will be determined as occurring prior to treatment with ORGN001 (pre-treatment), or as on or after first treatment (treatment-emergent), as described in [Section 8.3](#). Analyses of pre-treatment adverse events (PTAEs) and treatment-emergent adverse events (TEAEs) will be tabulated and presented separately. An incomplete date of AE onset will be compared to treatment start date, if unable to determine AE onset date is prior to treatment start, then AE will be considered a TEAE.

Subjects having multiple AEs within a category (e.g., overall, SOC, PT) will be counted once in that category. For severity/relationship tables, the subject's most severe/most related event within a category will be counted. Missing relationship to study drug will be considered treatment-related.

Percentages will be based on the total number of treated subjects in the Safety Set. Tables will be sorted by descending frequency of SOC and by descending frequency of PT within SOC. Listings will be provided for all TEAEs and PTAEs for the Safety Set. TEAEs with missing severity will not be included in the counts of patients within a SOC or PT; however, the event will be reported in listings.

AEs will include the displays described in the following sub-sections.

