6.5.3.1. Overall Summary of Adverse Events

All PTAEs and TEAEs will be presented using summary statistics (n, %). The number of subjects with events (n, %) will be displayed.

Table 2: Treatment-Emergent Adverse Events

Relationship	Severity
Related AEs (possibly, probably, or definitely related, missing/unknown)	Mild AEs
Not related AEs (not related or unlikely related)	Moderate AEs
	Severe AEs

Additionally, the number and percentage of subjects who withdrew from the study due to an AE, discontinued treatment due to an AE, or who died on study will be presented. These statistics will be presented for all TEAEs and separately, for SAEs.

6.5.3.2. Adverse Events and Serious Adverse Events by System Organ Class and Preferred Term

The number of PTAEs and TEAEs and the number and percentage of subjects with events will be presented by SOC and PT.

6.5.3.3. Adverse Events and Serious Adverse Events by System Organ Class, Preferred Term, and Relationship

The number and percentage of subjects with TEAEs will be presented by SOC and PT as described above by relationship (related, not related). If a patient has more than 1 occurrence of an AE, the strongest relationship to study treatment will be used in the summary table. SAEs will be summarized similarly.

6.5.3.4. Adverse Events and Serious Adverse Events by System Organ Class, Preferred Term, and Severity

The number and percentage of subjects with TEAEs will be presented by SOC and PT as described above by severity (mild, moderate, severe). If a subject has more than one occurrence of an AE, the most severe occurrence will be used in the summary table. SAEs will be summarized similarly.

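### SAP 6.5.3 leaves TEAEs with no severity grade out of the patient counts in every SOC and PT table, so reported incidence can fall but never rise

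*SAP*

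**What the plan says.** SAP 6.5.3 sets general counting rules before it introduces the displays in 6.5.3.1 to 6.5.3.5. Four of them bear on this point:

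- Missing severity: "TEAEs with missing severity will not be included in the counts of patients within a SOC or PT". The sentence goes on to say that the event is still listed.
- Missing relationship: "Missing relationship to study drug will be considered treatment-related".
- Unclear onset: "if unable to determine AE onset date is prior to treatment start, then AE will be considered a TEAE".
- Denominator: "Percentages will be based on the total number of treated subjects in the Safety Set".

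For the main table, SAP 6.5.3.2 says: "The number of PTAEs and TEAEs and the number and percentage of subjects with events will be presented by SOC and PT". SAP 6.5.3.3 (by relationship) and 6.5.3.4 (by severity) use the same SOC/PT layout, refer back to the rules above them, and treat SAEs in the same way. Table 2 in 6.5.3.1 places a missing or unknown relationship under related events. Under severity it has only mild, moderate and severe.

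Protocol 13.8.1 says: "All AEs will be summarized by both event counts and patient counts". It makes no exception for ungraded events. SAP 3.1, headed "Changes from Analyses Specified in the Protocol", is answered as not applicable (some text after that entry is redacted).

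**The concern.** Whether an event occurred and how severe it was are separate facts. A missing grade leaves the second unknown but not the first. The rule nevertheless removes the patient from the count of those who had the event.

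The study's primary objective is safety over the first 6 months. No endpoint is labelled primary, but the incidence and severity of AEs and SAEs is the first safety endpoint listed. No hypothesis test is planned, so the n (%) tables are themselves the safety result. With as few as 4 patients, one patient missing from a row changes how that row reads. The SAE tables follow the same rules, so an ungraded SAE could also drop out of the SOC/PT patient counts.

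**Working it through.** The documents give no AE rate, missing-grade rate or sample size calculation for this point, so there is no plan figure to reproduce. The check covers scope, direction, size and likelihood.

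**Scope.** The sentence stands in the general text of 6.5.3, ahead of the line that introduces the displays. The same section names the severity and relationship tables when it limits a rule to them (the most-severe/most-related rule), but this sentence names no table. Its object, patient counts within a SOC or PT, is what 6.5.3.2 and 6.5.3.3 report. Neither table needs a grade. On its wording the rule does not reach the overall summary in 6.5.3.1, the event counts in 6.5.3.2, pre-treatment AEs or the listings.

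**Direction.** The denominator is fixed at the Safety Set and a subject counts once per category. The rule can only take a subject out of the numerator, and only when all of that subject's TEAEs in the row are ungraded. Full enumeration confirms this. Take N = 4, one PT, and 0 to 2 TEAEs per subject, each graded or ungraded. That gives 6 states per subject and 6^4 = 1,296 configurations. In 2 of the 6 states (one ungraded event, or two ungraded events) the subject is lost.

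| Rule count minus true count | Configurations |
|---|---|
| 0 | 4^4 = 256 |
| -1 | 4 × 2 × 4^3 = 512 |
| -2 | 6 × 2^2 × 4^2 = 384 |
| -3 | 4 × 2^3 × 4 = 128 |
| -4 | 2^4 = 16 |

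The count is never above the truth. These are counts of configurations, not probabilities.

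**Size.** Shift per lost patient and row = 100/N percentage points. Only the minimum of 4 comes from the protocol (3.2 and 13.2); the other values are assumed.

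| N | 4 | 5 | 6 | 8 | 10 |
|---|---|---|---|---|---|
| Points | 25.0 | 20.0 | 16.7 | 12.5 | 10.0 |

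At N = 4, one patient whose only event in a PT is ungraded turns 1/4 (25%) into 0/4 (0%).

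**Likelihood.** Let p be the proportion of grades missing, independently and at random. A patient with k TEAEs in a row is dropped with probability p^k. Over M patient-by-PT rows with a single event each, the chance that at least one is dropped is 1 - (1 - p)^M, and the expected number is M × p. Both p and M are assumptions.

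| | p = 1% | p = 2% | p = 5% |
|---|---|---|---|
| Dropped, k = 1 | 1% | 2% | 5% |
| Dropped, k = 2 | 0.01% | 0.04% | 0.25% |
| At least one dropped, M = 20 | 18.2% | 33.2% | 64.2% |
| At least one dropped, M = 50 | 39.5% | 63.6% | 92.3% |
| Expected rows dropped, M = 50 | 0.5 | 1.0 | 2.5 |

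**Consistency with the rest of the plan.**

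1. Protocol 13.8.1 puts all AEs into the patient counts, the SAP rule does not, and the visible SAP 3.1 declares no change.
2. Missing relationship and unclear onset are both resolved towards counting the event. Missing severity alone is resolved towards not counting it.
3. The rule speaks of patients, while 6.5.3.2 also reports numbers of events. A row could therefore read 1 event in 0 patients.
4. The rule names TEAEs only. An ungraded event before the first dose, while the patient is still on rcPMP, is counted; the same ungraded event on ORGN001 is not.

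**The case against.** The strongest reply is that only the severity table was meant: the sentence turns on severity, and 6.5.3.4 is the one SOC/PT display that uses it. That is plausible, and on that reading overall incidence is unaffected. But the text does not say so, and a programmer works from the text. Even then, the mild, moderate and severe counts would not add up to the 6.5.3.2 count, so the sentence would still need rewording.

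Second, missing grades should be rare. Protocol 12.5.3 and 12.5.6 require the investigator to assess severity, monitors check AE documentation, and every TEAE is listed. In a study this small, a reader of the listings could find a dropped event. This stands as a limit on how often the rule will bite. It does not justify what the rule does when it bites, and a listing does not correct an n (%) table.

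Third, the protocol sentence leads into the handling of repeat occurrences, and protocol 13.10.1 lets the SAP specify missing-data handling. This softens the conflict but does not remove it. Section 13.10.1 concerns replacing or imputing values, whereas this rule discards a patient with a known event.

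Fourth, the clause about listings could mean that the event appears nowhere else, in which case event counts would fall too and the 1-event-in-0-patients row would not arise. The literal wording covers only patient counts, so the odd row follows from the text; the alternative reading would extend the loss to event counts.

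Last, the likelihoods rest on assumed inputs. At N = 4, 50 single-event rows means 50/4 = 12.5 per patient, and 20 rows means 5. They illustrate the range and are not estimates. Any redacted table shells might show how missing severity is displayed, but nothing visible does.

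**Conclusion.** The concern holds as stated. Read literally, SAP 6.5.3 makes the SOC/PT patient counts in 6.5.3.2, 6.5.3.3 and 6.5.3.4, and in their SAE versions, equal to or lower than the true counts. The shortfall is 100/N points per affected patient and row, with a ceiling of 25 at the minimum N of 4. It arises only if a grade is missing and the patient has no other graded TEAE in that row. With complete grading it is zero. Its direction and size per patient follow from the documents; its frequency cannot be derived from them.

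This should be fixed. It is a stated rule that gives the wrong incidence on a safety endpoint under the primary objective, always in the favourable direction. Confidence in the literal reading is high; what the sponsor intended cannot be established from the text.

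**What to change.** Replace the sentence in SAP 6.5.3 with:

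> TEAEs with missing severity are included in all overall, SOC, PT and relationship counts of subjects and events. In severity tables a subject is counted at the highest recorded grade in that category; a subject with no graded TEAE in that category is shown in a separate Missing category.

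Add a Missing row under Severity in Table 2 and a Missing category to the 6.5.3.4 displays. No grade is imputed, in keeping with the general approach in SAP 6.2.1.1, and the severity table then adds up to the SOC/PT table. In the example above, the row reads 1/4 (25%) instead of 0/4 (0%), and the shortfall is zero throughout.

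The cost is one SAP sentence and one extra category, with no new data. If any grade is missing, reported SOC/PT incidence may look less favourable; otherwise no count changes.

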6.5.3.1. Overall Summary of Adverse Events

All PTAEs and TEAEs will be presented using summary statistics (n, %). The number of subjects with events (n, %) will be displayed.

Table 2: Treatment-Emergent Adverse Events

Relationship	Severity
Related AEs (possibly, probably, or definitely related, missing/unknown)	Mild AEs
Not related AEs (not related or unlikely related)	Moderate AEs
	Severe AEs

Additionally, the number and percentage of subjects who withdrew from the study due to an AE, discontinued treatment due to an AE, or who died on study will be presented. These statistics will be presented for all TEAEs and separately, for SAEs.

6.5.3.2. Adverse Events and Serious Adverse Events by System Organ Class and Preferred Term

The number of PTAEs and TEAEs and the number and percentage of subjects with events will be presented by SOC and PT.

6.5.3.3. Adverse Events and Serious Adverse Events by System Organ Class, Preferred Term, and Relationship

The number and percentage of subjects with TEAEs will be presented by SOC and PT as described above by relationship (related, not related). If a patient has more than 1 occurrence of an AE, the strongest relationship to study treatment will be used in the summary table. SAEs will be summarized similarly.

6.5.3.4. Adverse Events and Serious Adverse Events by System Organ Class, Preferred Term, and Severity

The number and percentage of subjects with TEAEs will be presented by SOC and PT as described above by severity (mild, moderate, severe). If a subject has more than one occurrence of an AE, the most severe occurrence will be used in the summary table. SAEs will be summarized similarly.

6.5.3.5. Deaths, Other Serious Adverse Events, and Other Significant Adverse Events

All SAEs will be presented in subject listings. All AEs leading to study treatment withdrawal will be listed. A listing of subject deaths will be produced, if applicable.

6.5.4. Other Safety Analyses

6.5.4.1. Analyses for Laboratory Tests

Descriptive statistics by visit will be presented for each laboratory parameter and for changes from baseline.

Serum Chemistry	Hematology	Coagulation	Urinalysis
Sodium	Red blood cell count	Prothrombin time	Specific gravity
Potassium	Mean corpuscular volume	International Normalized Ratio	pH
Bicarbonate	Mean corpuscular hemoglobin		Glucose
Chloride	Mean corpuscular hemoglobin concentration		Protein
Blood urea nitrogen	White blood cell count		RBC (by dipstick)
Creatinine	Neutrophils (absolute and percentage)		Ketones (by dipstick)
Calcium	Lymphocytes (Absolute and percentage)		Urine protein to creatinine ratio
Alanine aminotransferase	Monocytes (absolute and percentage)		
Aspartate aminotransferase	Eosinophils (absolute and percentage)		

Serum Chemistry	Hematology	Coagulation	Urinalysis
Alkaline phosphatase	Basophils (absolute and percentage)		
Total bilirubin	Platelet count		
Serum osmolality	Hemoglobin		
Total Serum Albumin	Hematocrit		

For purposes of analyses, laboratory results based upon standardized units will be used. All laboratory values, where applicable, will be classified as normal, below normal, or above normal, and shift tables will be presented over time.

Scatter plots of all chemistry and hematology lab test values [REDACTED] by baseline values will be plotted. For hematology, the following tests will be plotted: RBC, WBC count, platelet count, hemoglobin, and hematocrit. All data will be presented in by-subject listings and flag for abnormal result will be included.

6.5.4.2. Vital Signs

Vital signs (systolic and diastolic BP, temperature, RR and HR) change from baseline, and percent change from baseline in vital signs will be summarized by visit and time point. Individual plots of systolic and diastolic BP measurements conducted [REDACTED] will be graphically displayed separately. Listings of vital signs will be produced and flag for abnormal result will be included.

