-  Collect venous blood samples [REDACTED] at EOI, 0.5, 1, 2, 3, and 5 hours post-EOI ( $\pm 5$  minutes for all time points).
-  Daily IV infusions of ORGN001 (24 hours  $\pm$  3 hours apart) occur either while in-patient or at home.
-  Changes in seizure medications, including the reason for the change, will be recorded.
-  Additional BP measurements are to be conducted prior to the infusion and at 30, 60, 90, and 120 minutes post-EOI, followed by hourly assessments until 6 hours post-EOI, then every 6 hours until the next dose.
-  Additional BP measurements are to be conducted prior to the infusion and hourly post EOI for 6 hours, then every 6 hours until the next dose. The SRC will review the blood pressure data along with all the other safety data to determine if continued frequent monitoring is needed.
-  An optional blood sample and urine sample will be collected at 24 hours after the EOI for PK and PD assessments.
- Abbreviations: AEs = adverse events; Bayley-III = Bayley Scales of Infant and Toddler Development-Third Edition; BP = blood pressure; CRF = case report form; EEG = electroencephalogram; eCRF = electronic case report form; EOI = end of infusion; GMFCS = Gross Motor Function Classification System; meds =

medications; MoCD = molybdenum cofactor deficiency; MRI = magnetic resonance imaging; PD = pharmacodynamics; PI = principal investigator; PK = pharmacokinetics; rcPMP = recombinant *E. coli*-derived cPMP; SRC = Safety Review Committee; SSC = S-sulfocysteine; WPPSI = Wechsler Preschool and Primary Scale of Intelligence.

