### 12.1 Vital Signs

Vital signs will be taken [REDACTED]. On Day 1, vital signs are to be taken within 24 hours prior to infusion. Vital signs will include heart rate, respiratory rate, BP, and temperature.

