For each subject, time on study from informed consent to last visit, study completion, termination or withdrawal (days) will be calculated as follows:

- For subjects who completed Month ■ = (date of Month ■ visit date – date of informed consent) + 1 day
- For subjects who withdrew prior to Month ■ = (date of study exit – date of informed consent) + 1 day

Additionally, for each subject, time on study from informed consent to last infusion will be similarly calculated.

Time on Study (months)

For each subject, time on study from informed consent to last visit, study completion, termination or withdrawal (months) will be calculated as follows:

- For subject who completed Month ■ = ((date of Month ■ visit date – date of informed consent) + 1 day)/30.4375, rounded to 1 decimal place
- For subjects who withdrew prior to Month ■ = ((date of study exit – date of informed consent) + 1 day)/30.4375, rounded to 1 decimal place

Additionally, for each subject, time on study from informed consent to last infusion will be similarly calculated.

Definition of Baseline Values

Baseline is defined as the last available assessment prior to treatment with ORGN001, except for growth parameters and blood and urine ■ where baseline is defined as the average of all available assessments on or prior to the date of first infusion with ORGN001.

Change from Baseline

Change from baseline will be calculated as follows:

Change of Baseline = Assessment Value – Baseline Assessment Value

Percent Change in Assessments from Baseline

Percent change in values from Baseline will be calculated as follows:

$$\% \text{ Change in Value} = \frac{(\text{Change in Value})}{\text{Baseline value}} \times 100$$

where Change in Value = (Assessment value – Baseline Assessment value), given that the baseline value is non-missing and non-zero and the subsequent value is non-missing.

Adverse Events

The analysis of AEs is described in detail in [Section 6.5.3](#). Subject percentages are based on the total number of treated subjects in the Safety Set.

Related AEs are defined as possible, probable, definitely related or unknown/missing. Unrelated AEs are defined as unlikely or not related.

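### Timed post-infusion blood pressure is summarised only against the pre-treatment baseline; change from the same-day pre-infusion reading should be added

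*SAP*

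**What the plan says.** SAP 6.5.4.2 covers systolic and diastolic BP, temperature, respiratory rate and heart rate, and plans that "change from baseline, and percent change from baseline in vital signs will be summarized by visit and time point". The same section adds individual plots of systolic and diastolic BP (the days plotted are redacted) and listings with abnormal values flagged.

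The baseline is set in SAP 8.3: "Baseline is defined as the last available assessment prior to treatment with ORGN001, except for growth parameters and blood and urine" markers. BP is not among the exceptions. The only change formula there is "Change of Baseline = Assessment Value – Baseline Assessment Value". Protocol 13.8.3 likewise plans changes from baseline by visit, with no same-day reference.

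The additional BP series are in Protocol Table 3 (Screening and Month 1). Footnote 33 reads "Additional BP measurements are to be conducted prior to the infusion and at 30, 60, 90, and 120 minutes post-EOI", then hourly to 6 hours and every 6 hours until the next dose. Footnote 34 reads "Additional BP measurements are to be conducted prior to the infusion and hourly post EOI for 6 hours", with six-hourly readings after that up to the following infusion. The days on which each applies are redacted.

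For routine vital signs, Protocol 12.1 states: "On Day 1, vital signs are to be taken within 24 hours prior to infusion".

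**The concern.** A reading just before the infusion, followed by readings timed from its end, allows a within-day contrast in which each child serves as his or her own control on that day. The SAP does not use it. The pre-infusion reading becomes one more time point, and every reading in the series is compared with a value from before the first dose. On a later day, the tabulated change therefore also contains whatever differed between that day and the baseline day.

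At stake is the precision and readability of one part of the final safety report. Safety is the primary objective (Protocol 2.1.1) and change from baseline in vital signs is a listed safety endpoint (Protocol 2.2.1). No hypothesis tests are planned and the minimum enrolment is 4 children, so the descriptive summaries are the analysis. A table whose spread is wider than the data require is less useful for judging whether BP moved after the infusion.

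**Working it through.** The documents give no BP variance and no power calculation, so there is no figure of the plan's to reproduce. The check compares the two references under a simple variance-components model.

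**Inputs**
- From the documents: one pre-treatment baseline for BP (SAP 8.3); a pre-infusion reading in each series (Protocol Table 3, footnotes 33 and 34); at least 4 patients (Protocol 13.2); descriptive analysis only (Protocol 13.1).
- Assumed, because the documents give no BP SDs: within-day SD w = 4 to 8 mmHg; between-day SD d = 2 to 8 mmHg; independent day effects and within-day errors; no drift.

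**Model for one child on a later series day**
- baseline reading = m + D0 + e0
- pre-infusion reading = m + D1 + e1
- post-infusion reading = m + D1 + effect + e2

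Here the D terms have SD d and the e terms have SD w.

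**Spread of change**
- From study baseline: effect + (D1 − D0) + (e2 − e0), so SD = sqrt(2(w² + d²)).
- From same-day pre-infusion: effect + (e2 − e1), so SD = sqrt(2) × w.
- Ratio = sqrt(1 + (d/w)²).

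The half-width below is that of a 95% t interval for a mean of 4: 3.182 × SD / sqrt(4). It is used only as a yardstick, since the plan makes no inference.

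| w | d | SD, study baseline | SD, same day | Ratio | Half-width, baseline | Half-width, same day |
|---|---|---|---|---|---|---|
| 8 | 2 | 11.7 | 11.3 | 1.03 | 18.6 | 18.0 |
| 6 | 6 | 12.0 | 8.5 | 1.41 | 19.1 | 13.5 |
| 4 | 6 | 10.2 | 5.7 | 1.80 | 16.2 | 9.0 |
| 4 | 8 | 12.6 | 5.7 | 2.24 | 20.1 | 9.0 |

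SDs and half-widths are in mmHg. Worked row (w = d = 6): sqrt(2 × 72) = 12.0; sqrt(2) × 6 = 8.5; ratio sqrt(2) = 1.41. A simulation of 4 children at w = d = 6 with a true effect of −8 mmHg gave SDs of 11.99 and 8.48, and a mean of −8.01 under both references. Without drift, the choice of reference affects spread and does not bias the mean.

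**Day 1.** If the series' pre-infusion reading is the last value before the first dose, it is the baseline. The two references are then identical and the ratio is 1.00.

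**What the planned table still gives.** Mean(post − baseline) − mean(pre − baseline) = mean(post − pre) when the same children contribute to both rows. The mean same-day change is therefore recoverable if the pre-infusion row is shown. Its SD is not, because that needs the covariance of the two changes, which is not tabulated. Its range is not recoverable from the summary either. Nor is its percent change, which has a different denominator for each child and day.

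**The case against.** The strongest case against the point is that little is lost.

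- SAP 6.5.4.2 plans individual BP plots and listings, which with about 4 children are the natural display of a within-day course. The redacted plot days may well be the series days.
- The mean effect can be recovered by subtraction.
- On Day 1 the references should coincide.
- The additional BP row appears in Table 3 only, and not in Tables 4, 5 or 6. The scheduled series therefore fall within about a month of baseline, and growth or ageing contributes little.
- At w = d = 6 mmHg the half-width is still 13.5 mmHg after the change, so neither table would reliably show a moderate effect in 4 children.

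All of this stands and limits the size of the point. It does not remove it: no planned summary contains a per-child same-day change, or its SD or range.

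A reader might infer three stronger things that the documents do not support.

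- **That an acute effect would be hidden.** The plots, the listings and the by-time-point layout keep the course available.
- **That the Safety Review Committee's decision on continued frequent BP monitoring would be affected.** Protocol 3.4 describes patient-level review while the study runs. The SAP describes summaries for the clinical study report and listings at database lock. Nothing says that the committee works from the SAP tables.
- **That same-day change should replace change from study baseline for the series.** Change from baseline is a protocol endpoint. A sustained shift in pre-infusion BP would disappear from a same-day-only summary.

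That the series is meant to detect an acute infusion effect is itself a fair inference from timing the readings to end of infusion. The documents state only the monitoring decision as its use.

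**Conclusion.** The point holds as a cheap improvement to the final safety report. For series days after Day 1, the only planned numerical summary of post-infusion BP carries between-day variation that an already collected reading would remove. The SD of change is inflated by a factor of 1.03 to 2.24 over the assumed SDs, and by 1.41 when within-day and between-day SDs are equal. The direction does not depend on those values: under the model there is some inflation whenever between-day variance is above zero.

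The size rests on assumed SDs, independence and no drift. The number of affected days is unknown because the series days are redacted. That at least one series falls after Day 1 is inferred from there being two different schedules. On Day 1 nothing changes, provided that the series' own pre-infusion reading counts as the last pre-treatment value. The SAP does not say so, and routine Day 1 vital signs may be up to 24 hours older (Protocol 12.1).

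**What to change.** In SAP 6.5.4.2:

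1. Keep change and percent change from study baseline as planned, for routine visits and for the BP series.
2. For each day with a post-infusion BP series, add a summary by time point of change from that day's pre-infusion reading, for systolic and diastolic BP.
3. For each child and series day, report the largest fall and the largest rise from that reading within 6 hours of end of infusion.
4. State in SAP 6.5.4.2 or 8.3 that the Day 1 series' pre-infusion reading is the Day 1 reference.

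The cost is SAP wording and one extra descriptive table. All readings are already scheduled, so no visit, measurement or study procedure changes.
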